6.4.11 Brief Rating Inventory of Executive Function (BRIEF, BRIEF-P, BRIEF-A)

The Behavior Rating Inventory of Executive Function (BRIEF™), preschool version, BRIEF-P, and adult version (used for subjects aged 19-35), are standardized, validated rating scales to measure executive function in children within the home and school environments that will be assessed by the parent according to the schedule in Table 1.

The BRIEF measures multiple aspects of executive functioning; scales include Inhibit, Shift, Emotional Control, Initiate, Working Memory, Plan/Organize, Organization of Materials and Monitor.

The original BRIEF was the basis for the development of the BRIEF-P. The BRIEF-P Rating Form consists of 63 items that measure various aspects of executive functioning: Inhibit Shift, Emotional Control, Working Memory, and Plan/Organize.

The BRIEF-A Rating Form consists of 75 items that measure various aspects of executive functioning. Nine overlapping scales are created in two different indexes. For the BRIEF-A, the BRI is composed of four scales: Inhibit, Shift, Emotional Control, and Self-Monitor. The Metacognition Index is composed of five scales: Initiate, Working Memory, Plan/Organize, Task Monitor, and Organization of Materials. The BRI and MI combine to yield the GEC Index.

For the BRIEF, BRIEF-P, and BRIEF-A, mean scores at Baseline, End of Study/ET and mean change from baseline to End of Study/ET, and descriptive statistics will be presented by treatment group and overall for the Safety population (SAF).

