1. If the total number of unanswered items is >14, do not compute any of the (eight) scale raw scores (INH, S, EC, INI, WM, PO, OM, m) for the BRIEF, as per the authors, the “protocol should be considered invalid”. In that case, all the scale raw scores will be missing, and the index scores will be missing as well.
2. If more than 2 (of the first 72) items have missing responses for a Scale (any of the 8 listed above), then a scale raw score should not be calculated. However, for any scale with 2 or fewer missing responses, impute a score of “1” for the missing item.
3. **IMPORTANT:** When calculating index scores, please first obtain the scale raw scores, and then the index scores are derived from the scale raw scores. Do not simply add up the scores for the individual questions.

References:

Programming Notes: Use the shell for 14.4.6.1 for the following tables.

Table 14.4.6.3
Behavior Rating Inventory of Executive Function-Adult Version (BRIEF-A) – Scoring summary table
Safety Population (De Novo Subjects)

Table 14.4.6.3.1
Behavior Rating Inventory of Executive Function-Adult Version (BRIEF-A) – Scoring summary table
Safety Population (De Novo Subjects) (Japan)

Scales are:

Inhibit
Shift
Emotional Control (EC)
Self Monitor
Initiate
Working Memory (WM)
Plan/Organize (PO)
Organization of Materials (OM)

For Indexes Part, where we use the 90% CI for the EOS/ET measurement, the following are used, along with relevant footnotes;

Behavioral Regulation Index (BRI)[1]
Metacognition Index (MI)[2]
Global Executive Composite (GEC) [3]

For the following line, include [4] as footnote
90% CI for change from BL[4]

[1] Computed as the sum of the scale raw scores obtained for Inhibit, Shift, Emotional Control, and Self Monitor.

[2] Computed as the sum of the raw scale scores obtained for Initiate, Working Memory, Plan/Organize, Organization of Materials, and Monitor.

[3] Computed as the sum of the raw scale scores for BRI and MI.

[4] Confidence interval of the mean change from baseline based on the t distribution.

Scales of the BRIEF-A

Scale	No. of items	Items	Scoring Instructions (for each individual)*

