Inhibit	8	5, 16, 29, 36, 43, 55, 58, 73	Add up scores for items on the scale
Shift	6	8, 22, 32, 44, 61, 67	Add up scores for items on the scale
Emotional Control	10	1, 12, 19, 28, 33, 42, 51, 57, 69, 72	Add up scores for items on the scale
Self-Monitor	6	13, 23, 37, 50, 64, 70,	Add up scores for items on the scale
Initiate	8	6, 14, 20, 25, 45, 49, 53, 62	Add up scores for items on the scale
Working Memory	8	4, 11, 17, 26, 35, 46, 56, 68	Add up scores for items on the scale
Plan/Organize	10	9, 15, 21, 34, 39, 47, 54, 63, 66, 71	Add up scores for items on the scale
Task Monitor	6	2, 18, 24, 41, 52, 75	Add up scores for items on the scale
Organization of Materials	8	3, 7, 30, 31, 40, 60, 65, 74	Add up scores for items on the scale
Validity scales			
Infrequency		10, 27, 38, 48, 59	Number of question responses where:(Question 10 = 3), (Question 27 = 1), (Question 38 = 3), (Question 48 = 1), Question 59 = 1) Number of questions meeting conditions: 0-2 is Acceptable. >= 3 is Infrequent.
Inconsistency	10 pairs	(2, 41), (25, 49), (28, 42), (33, 72), (34, 63), (44, 61), (46, 56), (51, 75), (60, 74), (64, 70).	For each item in a pair, obtain the score for each item, and subtract the scores, keeping the absolute difference. Sum the 10 absolute differences to get the Inconsistency score.

			Classification[1]: 0-7: Acceptable ≥ 8: Inconsistent
Negativity	10	1, 8, 19, 21, 22, 23, 29, 36, 39, 40	Count the number of items with a score of 3. That is the negativity score. Classification[1]: 0-5 Acceptable ≥ 6 Elevated

2. *Missing data handling for the BRIEF-A

1. If the total number of unanswered items is ≥ 1 in the Shift, Self-Monitor, and Task Monitor, the raw domain score is invalidated and won't be calculated.
2. If the total number of unanswered items is ≥ 2 in the Inhibit, Emotional Control, Initiate, Working Memory, Plan/Organize, and Organization of Materials, the raw domain score is invalidated and won't be calculated. However, for any scale with 1 missing responses, impute a score of "1" for the missing item.
3. **IMPORTANT:** When calculating index scores, please first obtain the scale raw scores, and then the index scores are derived from the scale raw scores. Do not simply add up the scores for the individual questions.

TLF Shells

Zogenix International Limited
ZX008-1503

LISTINGS

All listing displays for this open-label study are to be done by country and study site. Then by subject number.

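### The BRIEF-A table shell omits the Task Monitor scale and builds the Metacognition Index from a Monitor scale that the adult form does not have

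*SAP*

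**What the plan says.** SAP Section 6.4.11 defines the adult form. "The BRIEF-A Rating Form consists of 75 items that measure various aspects of executive functioning". The section then turns to how those items are grouped: "Nine overlapping scales are created in two different indexes". As to the Behavioral Regulation Index (BRI), "the BRI is composed of four scales: Inhibit, Shift, Emotional Control, and Self-Monitor". The MI is set out next: "The Metacognition Index is composed of five scales: Initiate, Working Memory, Plan/Organize, Task Monitor, and Organization of Materials". Last comes the composite, of which the section states: "The BRI and MI combine to yield the GEC Index".

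The shell for Tables 14.4.6.3 and 14.4.6.3.1 (the latter for Japan) lists eight scales: Inhibit, Shift, Emotional Control, Self Monitor, Initiate, Working Memory, Plan/Organize and Organization of Materials. Footnote [1] builds the BRI from Inhibit, Shift, Emotional Control and Self Monitor, in agreement with Section 6.4.11. Footnote [2] gives the MI as "Computed as the sum of the raw scale scores obtained for Initiate, Working Memory, Plan/Organize, Organization of Materials, and Monitor".

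The scoring table beneath that shell (Scales of the BRIEF-A) has nine scale rows. One is Task Monitor, with six items; none is called Monitor. The first missing-data rule after it also treats Task Monitor as a scored scale: "in the Shift, Self-Monitor, and Task Monitor, the raw domain score is invalidated and won't be calculated". The third rule tells the programmer to obtain the scale raw scores first and derive the indexes from them.

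The programming note above Listings 16.2.9.3.3 and 16.2.9.3.5, which also covers their Japan versions, asks for items to be arranged under eight scales. It serves both the school-age and the adult listings of individual responses.

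**The concern.** The shell is the instruction a programmer works from, and here it disagrees with both the definition in the SAP text and the scoring table printed under it. The sentence in footnote [2] also stands as footnote [2] of the school-age BRIEF (Tables 14.4.6.2 and 14.4.6.2.1). It is correct there, because that form has an eight-item Monitor scale. In the adult shell, footnote [1] was adapted and footnote [2] was not.

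At stake are one scale and two of the three index scores. The Task Monitor scale would not be reported, and the MI and GEC would rest on a component the adult form does not contain. Section 6.4 names BRIEF as the cognition measure among the safety assessments, BRIEF-A is its version for ages 19 to 35, and Table 14.4.6.3.1 is marked for the 2020 Japan report.

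**Working it through.** **Inputs.** Item lists come from the table Scales of the BRIEF-A, and index membership from Section 6.4.11. The item score range of 1 to 3 is stated in the programming notes for BRIEF-P and the school-age BRIEF. For BRIEF-A it is an assumption, supported by its Infrequency and Negativity rules, which use scores of 1 and 3.

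| Scale | Items | Index (Section 6.4.11) | In the shell's list |
|---|---|---|---|
| Inhibit | 8 | BRI | yes |
| Shift | 6 | BRI | yes |
| Emotional Control | 10 | BRI | yes |
| Self-Monitor | 6 | BRI | yes |
| Initiate | 8 | MI | yes |
| Working Memory | 8 | MI | yes |
| Plan/Organize | 10 | MI | yes |
| Task Monitor | 6 | MI | **no** |
| Organization of Materials | 8 | MI | yes |

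**Step 1: reproduce the plan's figure.** Nine scales: 8 + 6 + 10 + 6 + 8 + 8 + 10 + 6 + 8 = 70 items. Adding the five Infrequency items gives 75, and the lists cover items 1 to 75 exactly once each. The stated 75 items and nine scales therefore reproduce, but only with Task Monitor included. The shell's eight scales hold 70 − 6 = 64 items, or 69 with Infrequency.

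**Step 2: indexes as Section 6.4.11 defines them.**
- BRI = 8 + 6 + 10 + 6 = 30 items.
- MI = 8 + 8 + 10 + 6 + 8 = 40 items, raw range 40 to 120.
- GEC = 30 + 40 = 70 items, raw range 70 to 210.

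**Step 3: the three ways to read Monitor in footnote [2].**

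| Reading | MI | GEC | Error in level |
|---|---|---|---|
| Task Monitor | 40 items (40–120) | 70 items (70–210) | none |
| Dropped, as absent from the scale list | 34 items (34–102) | 64 items (64–192) | low by the Task Monitor score: 6 × 1 = 6 to 6 × 3 = 18 |
| Self-Monitor, the only monitor scale listed | 40 items (40–120) | 70 items (70–210) | Self-Monitor minus Task Monitor: 6 − 18 = −12 to 18 − 6 = +12 |

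Under the third reading the item counts look right, so a count would not reveal the error; Self-Monitor enters the GEC twice and Task Monitor not at all.

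**Step 4: changes from baseline.** The level errors do not carry over to change scores. If Monitor is dropped, the changes in MI and GEC omit the change in Task Monitor. If it is read as Self-Monitor, they are off by the Self-Monitor change minus the Task Monitor change. The document gives no data from which to size either.

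**Step 5: the row itself.** The shell's scale list has no Task Monitor entry, so the table lacks that row under all three readings.

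**The case against.** The strongest reply is that the SAP already contains the right answer. Section 6.4.11 names Task Monitor in the MI, the scoring table gives its items, and footnote [1] has already placed Self Monitor in the BRI. By elimination, Monitor in footnote [2] should mean Task Monitor, and a programmer who consults those places will get the MI and GEC right. Nor does footnote [2] license a four-scale MI, since it names five components. This stands: the two index errors are possible outcomes of an ambiguous shell, not certain ones. It does not restore the missing row, and the shell should not depend on the programmer noticing a name that does not match.

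The reach is also limited. The tables are restricted to de novo subjects. The shells' treatment-group table puts these at about 35 of all ages, so the adults can hardly exceed that. The output is descriptive: n, mean, standard error and, for the indexes, a 90% confidence interval for change. No test or decision depends on it. That stands as well.

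A reader might further infer that the BRIEF-A missing-data rules conflict, because the first voids Shift, Self-Monitor and Task Monitor when any item is missing, while the second ends by imputing 1 when a scale has one missing response. The document does not support this. The imputation sentence follows directly on the second rule's list of six other scales and qualifies that rule's threshold of two missing items, so the two rules form one consistent procedure.

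**Conclusion.** The shell is wrong as written on two counts: Task Monitor is absent from its scale list, and footnote [2] names a scale BRIEF-A does not have. The missing row is certain. The error in the MI and GEC is conditional: none if Monitor is read as Task Monitor, 6 to 18 points low in level if it is dropped, and between −12 and +12 if it is read as Self-Monitor. These ranges assume 1-to-3 item scoring for BRIEF-A.

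A reader might infer that the MI and GEC will necessarily be wrong. That goes too far, because the SAP text and the scoring table both point to the correct reading. The BRI is unaffected, and so are the school-age BRIEF and BRIEF-P. The matter is worth correcting because it is a scoring instruction for a safety output, but it concerns a small adult subgroup and no inference.

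**What to change.** In the shell for Tables 14.4.6.3 and 14.4.6.3.1, add Task Monitor to the list of scales. Change footnote [2] to Initiate + Working Memory + Plan/Organize + Task Monitor + Organization of Materials. In the programming note that covers Listings 16.2.9.3.5 and 16.2.9.3.5.1, ask for nine scales for BRIEF-A and keep eight for the school-age BRIEF.

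The missing-data rules and footnote [1] need no change. The cost is shell wording only: no new data, analysis or sample-size consequence. If any BRIEF-A output has already been programmed from this shell, check which scale was used as Monitor.

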Programming note: Use the shell for 16.2.4.3 for

Listing 16.2.4.3.1
Prior and concomitant medications and therapies/treatments (Japan)

Listing 16.2.4.4.1
Prior antiepileptic Drugs (AEDs)

Subject Identifier	Medication /ATC Classification [1]	Type of treatment	Route	Dose	Frequency*	Start Date/Day#	Stop Date/Day#
XXXX	TEXT	Non-medication	TEXT	TEXT	B1M1 BID PRN Q4H Q6H Q12H Q24H QID QM	DDMMYYYY/XX	DDMMYYYY/XX Ongoing
	& TEXT	Risk medication					

* B1M1 = Twice per month, BID = Twice per day, PRN = As needed, Q4H = Every four hours, Q6H = Every Six hours, Q12H = Every Twelve hours, Q24H = Every Twenty-four hours, QID = Four times a day, QM = Every Month. Qd or QD=Daily, or Everyday, or once a day.

Relative to first dose of study treatment.

& Prior medication.

[1] WHO Drug Dictionary

Programming note: Use the shell for 16.2.4.4.1 for the following listings.

Listing 16.2.4.4.2
Concomitant antiepileptic Drugs (AEDs)

Listing 16.2.4.4.3
Prior antiepileptic Drugs (AEDs) (Japan)

Listing 16.2.4.4
Concomitant antiepileptic Drugs (AEDs) (Japan)

Listing 16.2.4.5
Rescue medications

Listing 16.2.4.5.1
Rescue medications (Japan)

Listing 16.2.5.1
IMP Intake per day during Treatment

Country:

Subject Identifier	Date+Time	Study Day#	Epoch	Dose Taken? (None/Partial/Full)
XXXX				
XXXX				
.				
.				
.				

Relative to first dose of study treatment.

[1] Study date and time is the time the dose was entered into diary

[2] Study medication was administered twice daily, and compliance was recorded each time in the eDiary as full, partial or none.

Programming note: Use the shell for 16.2.5.1 for

Listing 16.2.5.1.1
IMP Intake per day during Treatment (Japan)

Listing 16.2.5.2
 IMP Intake – self reported % compliance

Treatment group: xxx
 Subject Identifier: <subject no.> Age: <> Sex:<x>

Study Week	Day1	Day2	Day3	Day4	Day5	Day6	Day7	Compliance %
1								
2								
3								
4								
Month1								Xxx.xx%
5								
6								
7								
8								
Month2								xxx.x%
...								
.....								

Note: Study medication was administered twice daily, and compliance was recorded each time in the eDiary as full, partial or none. (See Listing 16.2.5.1) From this, compliance was calculated by assuming that a missed dose=0% of dose consumed, partial=50%, full=100%.

Programming Note: from daily diary record.

Programming note: Use the shell for 16.2.5.2 for

Listing 16.2.5.2.1
 IMP Intake – self reported % compliance (Japan)

Listing 16.2.5.3
Drug Accountability and Compliance to Study Treatment by Visit

Treatment group: xxx

Subject Identifier	Visit	Bottle Number	Amount Of volume Dispensed	Date/Day# Dispensed	Amount of Volume Returned	Date/Day# Returned
XXXX	V1, etc.	XXXXXX XXXXXX NA	XXX XXX TEXT NA	DDMMYYYY/XX DDMMYYYY/XX NA	NA DDMMYYYY/XX	
XXXX						
XXXX						
.						
.						
.						

Relative to first dose of study treatment.

Programming Notes: Use 28 days, keep in ADEC. Use the shell for 16.2.5.3 for

Listing 16.2.5.3.1
Drug Accountability and Compliance to Study Treatment by Visit (Japan)

Listing 16.2.6.1
 Convulsive seizure – duration and number of occurrences per subject (Diary data)

Randomized Treatment: XXX

Subject Identifier	Period	Seizure Date/Study Day**	Time of Seizure	Single/ Cluster/Discrete	Type of convulsive seizure	Duration of seizure	Approximate duration of cluster	Number of seizures
XXXX	<Baseline(Core)> <Core Study(T+M)> <OLE Treatment>	Yyyy-mm-dd Yyyy-mm-dd Yyyy-mm-dd		<Single, or Cluster>	Type 1 Type 2 Type 3 ...	<2 min 2-10 min >10min		1 2 3* 4 ...
XXXX								
XXXX								
.								
.								
.								

*Note: Clusters of seizures could be recorded by duration, by number of seizures, or both. When reported by duration only, the number of seizures was set equal to 3 for analysis.

**With reference to start of OLE Study

Programming note: Present the subject identifier (grayed out) on all lines after the first line for a subject.

Convulsive seizures:

- A: HEMICLONIC (Note lateralization: R body, L body, or independent R and L)
- B1: FOCAL WITH CLEAR OBSERVABLE MOTOR SIGNS (i.e. automatisms, dystonic posturing, focal tonic stiffening)
- C: SECONDARILY GENERALIZED TONIC CLONIC (evolving to bilateral convulsive seizure from focal seizure)
- D: GENERALIZED TONIC CLONIC CONVULSION
- G: TONIC
- I: CLONIC (Note bilateral: symmetric R and L)
- J: TONIC/ATONIC (cannot differentiate) - 'drop attacks' should be placed here

Use the shell fo 16.2.6.1 for

Listing 16.2.6.1.1

Convulsive seizure – duration and number of occurrences per subject (Diary data) (Japan)

Listing 16.2.6.2

Non-Convulsive seizure – by type, duration and number of occurrences per subject (Diary data)

Treatment group: XXX

Subject Identifier	Period	Seizure Date/Study Day**	Single/ Cluster	Type of non-convulsive seizure	Duration of seizure	Approximate duration of cluster	Number of seizures
XXXX	Baseline(Core)	Yyyy-mm-dd	<Single, or Cluster>	Type 1	<2 min		1
	Core Study(T+M)	Yyyy-mm-dd	Single, or Cluster>	Type 2	2-10 min		2
	OLE Treatment	Yyyy-mm-dd	Single, or Cluster>	Type 3	>10min		3*
				...			4
							...
XXXX							
XXXX							
.							
.							
.							

*Imputed – the number of seizures in the cluster was not stated. It was imputed as 3.

**With reference to start of OLE Study.

Programming note: Present the subject identifier (grayed out) on all lines after the first line for a subject.

Non-convulsive Seizures:

B2: FOCAL WITHOUT CLEAR OBSERVABLE MOTOR SIGNS (i.e. autonomic changes like color change or pupillary dilation, and no motor signs)

E: ABSENCE OR ATYPICAL ABSENCE

F: MYOCLONIC

H: ATONIC – not resulting in a drop

K: INFANTILE SPASMS (if under 3 years of age)

L: EPILEPTIC SPASMS (if 3 years of age and older)

TLF Shells

Zogenix International Limited
ZX008-1503

M: NON CONVULSIVE STATUS (greater than 30 min)

O: OTHER

Programming Note: Use the 16.2.6.2 shell for

Listing 16.2.6.2.1

Non-Convulsive seizure – by type, duration and number of occurrences per subject (Diary data) (Japan)

Listing 16.2.6.3

Duration of the Longest interval between convulsive seizures and convulsive seizure free days per subject

Treatment group: XXX

Subject Identifier	Period	Number of Days with a Seizure Occurrence	Longest interval between convulsive seizures	Convulsive seizure free days
XXXX	Baseline(Core)	Xxx	xx	XX
	Core Study(T+M)	Xxx	Xxx	Xxx
	OLE Treatment	xxx	xxx	xxx
XXXX				
XXXX				
.				
.				
.				

Programming Note: Present the subject identifier (grayed out) on all lines after the first line for a subject. Use the 16.2.6.3 shell for

Listing 16.2.6.3.1

Duration of the Longest interval between convulsive seizures and convulsive seizure free days per subject (Japan)

Listing 16.2.6.4
 Percent reduction in convulsive seizure frequency from baseline

Treatment group: XXX

Subject ID	mITT Population?	Period	CSF per 28 Days	% Change from Baseline(Core)	≥25%? (Y/N)	≥50%? (Y/N)	≥75% (Y/N)	=100%? (Y/N)
XXXX	Y	Baseline (Core)	xxx.x					
		Core Study (T+M)	xxx.x	xxx.x	Y	N	Y	N
		Month1-EOT	xxx.x	xxx.x	Y	Y	N	N
		Month2-EOT	xxx.x	xxx.x	Y	N	N	N
XXXX	Y	Baseline (Core)	xxx.x					
		Core Study (T+M)	xxx.x	xxx.x	Y	Y	Y	N
		Month1-EOT	xxx.x	xxx.x	Y	Y	Y	N
		Month2-EOT	xxx.x	xxx.x	Y	Y	Y	N
XXXX	Y	Baseline (Core)	xxx.x					
		Core Study (T+M)	xxx.x	xxx.x	Y	Y	Y	N
		Month1-EOT	xxx.x	xxx.x	Y	Y	Y	N
XXXX	Y	Month2-EOT	xxx.x	xxx.x	Y	Y	Y	Y

Programming Note: Present the subject identifier (grayed out) on all lines after the first line for a subject.
 Use the 16.2.6.4 shell for

Listing 16.2.6.4.1
 Percent reduction in convulsive seizure frequency from baseline (Japan)

Listing 16.2.6.5

Clinical Global Impression – Improvement rating as assessed by the Parent/Caregiver and Investigator

Subject Identifier	Age/sex	Assessment Date	Clinic Visit	Analysis Visit	CGI score by parent/caregiver	CGI score by Investigator
XXXX				Visit 1, Visit 3, Visit 4, Visit 5, Visit 6, Visit 7, Visit 8,	Very much improved Much improved Minimally improved No change Minimally worse Much worse Very much worse	Very much improved Much improved Minimally improved No change Minimally worse Much worse Very much worse
				Visit 12		
XXXX			
XXXX						
.						

[figure not shown]
Note: CGI = Clinical Global Impression

Programming note: Present the subject identifier (grayed out) on all lines after the first line for a subject. Use the shell for 16.2.6.5 for

Listing 16.2.6.5.1

Clinical Global Impression – Improvement rating as assessed by the Parent/Caregiver and Investigator (Japan)

Listing 16.2.6.7
Quality of life of the Parent/Caregiver using EQ-5D-5L scale

Subject Identifier	Age/Sex	Visit	Assessment Date/Day #	Was the assessment done		Response
XXXX		Baseline	DDMMYYYY/XX	Yes		XXXXXX
				No		XXXXXX
		End of study visit				XXXXXX
		XXXXXX				
						XXXXXX
						XX
XXXX		
XXXX						
.						
.						

Listing 16.2.6.8
Quality of life of the Parent/Caregiver using HADS scale

Subject Identifier	Visit [1]	Was the assessment done	Response
XXXX	Baseline Visit 1		XXXXX
			XXXXX
			XXXXX
	Visit 3		XXXXX
	Visit 4		XXXXX
	Visit 5		XXXXX
	---		XXXXX
	---		XXXXX
	---		XXXXX
	---		XXXXX
XXXX	Visit 12	XXXXX	
	...	XXXXX	
XXXX			

[1] repeated for Visit 1 and each clinical visit from Visit 3 through Visit 16

Programming note: This table for ZX008 – 1501 and ZX008-1502 subjects only. Do not include ZX008-1504 Cohort 2

Listing 16.2.6.9.1
Pediatric Quality of Life Inventory (Peds QL)- for TODDLERS (age 2-4 years)

Treatment Group: ZX008 OL

Subject Identifier	Visit [1]		Response
XXXX	Baseline Visit 1		AVALC
			XXXXX
	Visit 3		XXXXX
			XXXXX
			XXXXX
			XXXXX
			XXXXX
			XXXXX
	---		XXXXX
	XXXXX		
Visit 12	...		
XXXX	
XXXX			
.			
.			
.			

[1] Repeated for Visit 1 and Visit 3 through Visit 16

TLF Shells

Zogenix International Limited
ZX008-1503

Programming Notes: Use Listing shell 16.2.6.9 for below listings:

Listing 16.2.6.9.2

Pediatric Quality of Life Inventory (Peds QL) - for Young Children (age 5-7 years)

Listing 16.2.6.9.3

Pediatric Quality of Life Inventory (Peds QL) - for Children (age 8-12 years)

Listing 16.2.6.9.4

Pediatric Quality of Life Inventory (Peds QL) - for TEENS (age 13-18 years)

Listing 16.2.6.9.5

Pediatric Quality of Life Inventory (Peds QL) – Family Impact Module

Listing 16.2.6.10
Study Medication Palatability Assessment

Treatment Group: ZX008 OL

Subject Identifier	Age/Sex	Visit	Was the assessment done	Question	Response
XXXX		Visit 3	Yes No	1 – Over the past month, on the basis of the reaction / facial expression of your child, do you think that the medicine’s taste and texture are acceptable/not acceptable to your child?	XXXXXX
				2 – Over the past month, please rate [1]how much your child likes/dislikes the medicine’s taste	XXXXXX
				3 - Over the past month, do you sometimes have problems giving the medicine to your child due to its taste or texture?	XX
XXXX			
XXXX					
.					
.					
.					

[1]Rating scale: 5=likes it very much; 4=likes it; 3=neither likes or dislikes it; 2=dislikes it; 1=dislikes it very much

Listing 16.2.6.11
Sleep quality and mealtime behavior

Treatment Group: ZX008 OL

Subject Identifier	Age/Sex	Visit	Date of Assessment /Day #	Sleep Quality Question Response	Mealtime Behavior Question Response
XXXX	xxx/x	Visit 3	DDMMYYYY/XXX	More Disturbed Same Better	Worse Behavior Not Changed Improved Behavior
XXXX				...	
XXXX					
.					
.					
.					

Note: This scale is collected only for subjects from core study ZX008-1504.
Relative to first dose of study treatment.

Listing 16.2.6.12
Karolinska sleepiness scale

Treatment Group: ZX008 OL

Subject Identifier	Age/Sex	Visit	Date of Assessment /Day #	
XXXX	xxx/x	Visit 3	DDMMYYYY/XXX	
XXXX				
XXXX				
.				
.				
.				

Note: This scale is collected only for subjects from core study ZX008-1504.

Relative to first dose of study treatment.

[1] Values 1 – 6 are categorized as Alert. Values 7 – 9 are categorized as sleepy.

TLF Shells

Zogenix International Limited
ZX008-1503

Listing 16.2.7.1
Adverse Events

Subject Identifier	Age/ Gender/ Race	Adverse Event (System Organ Class/ Preferred Term)	Start Date/ Day#	stop Date/ Day#	Related to study Drug	Severity	Action Taken with Study treatment	Other Action Taken	Outcome	Serious
XXXX	Xx/ X/ x	& TEXT (SOC/PT)	DDMMYYYY /XX	DDMMYYYY /XX	Yes No	Mild Moderate Severe	Dose not changed Dose increased Dose reduced Drug Interrupted Drug Withdrawal NA	None withdrawn from study Treated with Medication Other: TEXT	Not resolved Resolved Resolved w/sequelae Resolving Unknown Fatal	Yes: Death Life- Threatening Hospitalization Disability/Permanent Damage Congenital Anomaly/Birth defect Medically significant No
XXXX										
XXXX										
.										
.										
.										

Relative to first dose of study treatment.
& Treatment-emergent adverse event.
NA = Not applicable

TLF Shells

Zogenix International Limited
ZX008-1503

Programming note:

Use the shell for 16.2.7.1 for the following listings:

Listing 16.2.7.1.1 Adverse events (Japan)

Listing 16.2.7.2 Adverse events of special interests (AESI)

Listing 16.2.7.2.1 Adverse events of special interests (AESI) (Japan)

Note: Please record only Adverse event of special interest as per definition provided in Protocol

Listing 16.2.8.1.1
Laboratory Data: Hematology parameters

Subject Identifier	Visit	Sample Date/Day# and	Parameter	Value*	Reference Range	Unit
XXXX	Screening (Visit 1)	DDMMYYYY/XX	Haemoglobin	XX.X H	XX.X-XX.X	TEXT
	Visit 2	ND: TEXT	Haematocrit	XX.X L		
	Visit 3		...	XX.X		
	Visit 4			...		
	Visit 5					
	Visit 6					
	... Visit 12					
XXXX						
XXXX						
.						
.						
.						

ND = Not Done.

Relative to first dose of study treatment.

* H = Above reference range, L = Below reference range

Programming Notes: Use the shell for 16.2.8.1.1 for the following listings:

Listing 16.2.8.1.1.1
Laboratory Data: Hematology parameters (Japan)

Listing 16.2.8.2.1
Laboratory Data: Biochemistry parameters

Listing 16.2.8.2.1.1
Laboratory Data: Biochemistry parameters (Japan)

Listing 16.2.8.3
Laboratory Data: Coagulation parameters

Listing 16.2.8.3.1
Laboratory Data: Coagulation parameters (Japan)

Listing 16.2.8.4.1
Laboratory Data: Urinalysis parameters

Listing 16.2.8.4.1.1
Laboratory Data: Urinalysis parameters(Japan)

For Listing 16.2.8.4 and 16.2.8.4.1, Urinalysis – add column “Result” (as 5th column) with result “Normal” or “Abnormal”.

Listing 16.2.8.5
Tests of growth, precocious puberty and Thyroid Function

Listing 16.2.8.5.1
Tests of growth, precocious puberty and Thyroid Function (Japan)

Programming Notes: Please use **STLB11** from ISS but only include Baseline (OLE) through End of Study in OLE for the following listings.

Listing 16.2.8.1.2

Most Abnormal Laboratory Parameters during Open-label Treatment Period - Hematology

Listing 16.2.8.1.2 .1

Most Abnormal Laboratory Parameters during Open-label Treatment Period - Hematology (*Japan*)

Programming Notes: Use shell for ISS STL12 but only include Baseline (OLE) through End of Study in OLE for the following listings.

Listing 16.2.8.2.2

Most Abnormal Laboratory Parameters during Open-label Study Periods – Biochemistry

Listing 16.2.8.2.2.1

Most Abnormal Laboratory Parameters during Open-label Study Periods – Biochemistry (*Japan*)

Programming Notes: Please use shell for ISS Listing STL13 but only include Baseline (OLE) through End of Study in OLE for the following listings.

Listing 16.2.8.4.2

Most Abnormal Laboratory Parameters during Open-label Study Periods -- Urinalysis

Listing 16.2.8.4.2.1

Most Abnormal Laboratory Parameters during Open-label Study Periods -- Urinalysis (*Japan*)

Use shell from 16.2.8.2.2 – add column “Result” (as 5th column) with result.

TLF Shells

Zogenix International Limited
ZX008-1503

Listing 16.2.8.6
Urine Pregnancy Test

Subject Identifier	Was Pregnancy test performed	Date of Urine pregnancy test / (Visit)	Result
XXXX	NA(female of non-child bearing potential)	DDMMYYYY/Visit X	Negative
	Not Done		Positive
	Done		
XXXX			
XXXX			
.			
.			
.			

Relative to first dose of study treatment.

TLF Shells

Zogenix International Limited
ZX008-1503

Programming Notes: Use the shell for 16.2.8.6 for the following:

Listing 16.2.8.6.1
Urine Pregnancy Test (Japan)

Listing 16.2.8.7
Urine THC panel

Listing 16.2.8.7.1
Urine THC panel (Japan)

Listing 16.2.8.8
Whole blood cannabidiol

Listing 16.2.8.8.1
Whole blood cannabidiol (Japan)

Listing 16.2.9.1.1
Vital Signs

Treatment group: xxx

Subject Identifier	Age/Sex	Visit	Visit Date/Day#	Systolic Blood Pressure (mmHg)	Diastolic Blood Pressure (mmHg)	Heart Rate (bpm)	Respiratory (Breaths/min)	Body Weight (kg)	Body Height (cm)	BMI (kg/m ²)	Temperature (C)		
XXXX	XX/X	Screening (Visit 1)	DDMMYYYY/XX	XXX	XXX	XXX	XXX	XXX	XXX	XXX	XXX		
		Visit 2		XXX	XXX	XXX	XXX	XXX	XXX	XXX	XXX		
		Visit 3		XXX	XXX	XXX	XXX	XXX	NA	XXX	XXX		
		Visit 4		XXX	XXX	XXX	XXX	XXX	NA	XXX	XXX		
		Visit 5		XXX	XXX	XXX	XXX	XXX	NA	XXX	XXX		
		Visit 6		XXX	XXX	XXX	XXX	XXX	NA	XXX	XXX		
		Visit 7		XXX	XXX	XXX	XXX	XXX	XXX	XXX	XXX		
		Visit 8		XXX	XXX	XXX	XXX	XXX	XXX	XXX	XXX		
			XXX	XXX	XXX	XXX	XXX	NA	XXX	XXX		
		Visit 16		XXX	XXX	XXX	XXX	XXX	XXX	XXX	XXX		
		XXX											
		XXXX											
.													

